4. STUDY DESIGN

4.1. General Design

This study will be a Phase 3, randomized, observer-blinded, active-controlled trial to evaluate the safety and efficacy in preventing seasonal influenza of mRNA-1010 in adults 50 years and older.

The vaccine to be tested includes mRNAs encoding for the surface glycoproteins of the strains recommended by the WHO for 2022-2023 NH cell- or recombinant-based vaccines:

- A/Wisconsin/588/2019 (H1N1)pdm09-like virus;
- A/Darwin/6/2021 (H3N2)-like virus;
- B/Austria/1359417/2021 (B/Victoria lineage)-like virus; and
- B/Phuket/3073/2013 (B/Yamagata lineage)-like virus.

Immunizations are planned during the typical 2022/2023 NH vaccination campaign period. However, if the targeted number of reverse transcriptase-polymerase chain reaction (RT-PCR)-confirmed ILI cases observed are not reached, an extension of enrollment over multiple influenza seasons may be required. As a result, vaccines with other seasonal-specific compositions may be used and administered during the relevant typical vaccination campaigns, as appropriate. Additionally, if the interim vaccine effectiveness analyses by public health authorities demonstrate noneffectiveness of licensed influenza vaccines, sample size re-estimation and continuation of enrollment into the next season may be considered.

Approximately 23,000 participants will be randomized in a 1:1 ratio to receive a single dose of mRNA-1010 at **CC1** µg total mRNA or a single dose of the active comparator. Randomization will be stratified by age categories (≥ 50 to < 65 years or ≥ 65 years) and influenza vaccine status in the previous influenza season (received or not received) at the time of screening. At least 50% of enrollees will be ≥ 65 years old, including at least 10% who will be ≥ 75 years old.

Table 3: Vaccination Groups and Dose Levels

Vaccination Group	Vaccination Received	mRNA/Antigen	Total Dose (µg)	Number of Participants
		HA (each) (µg)		
1	mRNA-1010	CC1 (of mRNA)	CC1 (of mRNA)	11,500
2	Active Comparator (Fluarix®)	CC1 (of protein)	CC1 (of protein)	11,500

Abbreviations: HA = hemagglutinin; mRNA = messenger ribonucleic acid.

Clinic visits for all participants will comprise a Screening visit (up to 28 days before the Day 1 visit, or maybe on the same day as the Vaccination Visit on Day 1) and a Vaccination Visit (Day 1) as showed in the schedule of events (SoE, [Table 1](#)).

For participants aged 65 years and older, frailty will be assessed by clinic staff at baseline using the Edmonton Frail Scale (EFS).

Approximately 1000 participants will be asked to provide blood samples at baseline and on Day 29 (28 days post vaccination) for assessment of immune responses to the study intervention

(immune response biomarker subset). A clinic visit on Day 29 will be required for these participants. All participants will be asked to complete an electronic diary (eDiary) for solicited ARs from Day 1 to Day 7. All participants will be asked to provide an optional blood sample for future research use at Day 1.

There will be 6 safety telephone call visits at Days 8, 29 (except for those participants who are not in the immune response biomarker subset which requires a clinic visit on Day 29), 91, 181, 271, and 361 (Month 12)/EoS as specified in the SoE. The study duration (including screening) is up to 13 months for each participant and the total study duration is approximately 27 months (if 2 influenza seasons are required to perform efficacy analyses).

Participants will be instructed to report whether ILI symptoms have been experienced, via a Symptom Reporting eDiary, twice weekly from Day 1 to Day 181 and once weekly from Day 182 to Day 361 (Month 12)/EoS. If participants experience ILI symptoms, they will be instructed to enter the details in the eDiary and contact the clinic to determine if an NP swab should be collected for RT-PCR testing. NP swabs for testing should be collected within 72 hours of symptom onset. Sites should also reach out to participants if illness symptoms are noted upon review of the eDiary to assess whether the participant is required to provide an NP swab.

NP swab should be collected prior to any antiviral therapy if possible. NP swabs may be collected as part of a home visit in lieu of a clinic visit. In the event that NP swabs during ILI cannot be collected, any available influenza testing results performed outside of the study should be captured in the electronic case report form (eCRF).

Unscheduled clinic visits for ILI symptoms and viral respiratory panel testing may be conducted. Participants who manifest protocol-defined ILI or for those participants who experience ILI symptoms but have not yet fulfilled protocol-defined ILI, and based on Investigator's discretion when influenza is suspected, will be evaluated by real-time RT-PCR testing of NP swab specimen(s) for influenza and other respiratory pathogens. NP swabs may be collected as part of a home visit in lieu of a clinic visit.

All participants who report symptoms of ILI will receive eDiary prompts to complete patient-reported outcome questionnaires for EuroQoL 5 Dimension 5-Level (EQ-5D-5L) and Work Productivity and Activity impairment Questionnaire: Influenza-like Illness (WPAI:ILI).

The Investigator might ask a participant to return to the clinical site for an unscheduled visit under certain situations (eg, if an AE is reported). Additional assessments, as necessary, may be conducted at these visits to ensure the safety and well-being of participants during the study. Electronic case report forms should be completed for each unscheduled visit.

All personnel involved in the conduct of the study will remain blinded to individual treatment assignment until planned study unblinding, except for appropriately delegated unblinded pharmacists, vaccine administrators, and monitors. The participant, Investigator, and clinical staff responsible for study assessments/safety will not have access to the treatment assignment during the conduct of the study. The Investigator may be unblinded in the event of an emergency (refer to [Section 6.3.7](#)).

4.2. Scientific Rationale for Study Design

This trial is designed as an observer-blind trial. Participants will receive a single dose of either mRNA-1010 vaccine or a licensed quadrivalent seasonal influenza vaccine (an active comparator) in order to assess safety and efficacy of the vaccine.

In this observer-blind trial, participants, clinic staff involved in participant assessment, and Sponsor personnel (or its designees) will be blinded to participant vaccine allocation. A limited number of Sponsor and/or contract research organization (CRO) personnel will be unblinded to conduct safety data analyses for the DSMB safety data reviews (as described in the DSMB charter) and perform the primary analysis. Unblinded study personnel, who will not participate in any other aspect of the trial, will perform study intervention accountability, dose preparation, and study intervention administration.

The NP swab specimen(s) for assessment of pathogens, including influenza virus and severe acute respiratory syndrome coronavirus 2 (SARS-CoV-2), will be collected any time from Day 1 through Day 361 (Month 12)/EoS if the participants have protocol-defined ILI (see [Section 8.10.5](#)) or if deemed necessary per Investigator's discretion when influenza is suspected. If participants experience these signs or symptoms, they will be instructed to contact the clinic to determine if an NP swab is required to be collected for testing. NP swabs may be collected as part of a home visit in lieu of a clinic visit. If NP swabs during ILI cannot be collected, any available influenza testing results performed outside of the study should be captured in the eCRF.

4.3. Justification for Dose, Control Product, and Choice of Study Population

The selection of the **CC** µg dose level of mRNA-1010 is supported by the data from the Phase 1/2 and the Phase 2 NH interim analyses. First, the **CC** µg dose level elicited strong HAI antibody responses. The geometric mean titers (GMTs) exceeded the 1:40 titer threshold for the 2 influenza A strains and 2 influenza B strains tested. This threshold was previously correlated with a 50% reduction in risk of influenza virus infection. This dose generated robust HAI responses for H1N1 and H3N2 strains with Day 29 GMTs that were higher than the licensed comparator. Second, the **CC** µg dose level demonstrated an acceptable reactogenicity and safety profile. The frequencies of solicited ARs were lower in the **CC** µg dose level than those of the **CC1** µg and **CC2** µg dose levels while the immunogenicity was comparable. The reactogenicity and safety profile of the **CC** µg dose level was not substantially different to that of the **CC** µg dose level, whereas the immunogenicity was higher particularly for adults 50 years and older. In summary, the safety and immunogenicity profile observed from the mRNA-1010-P101 study supports selecting mRNA-1010 at a **CC** µg dose level for this study. Further details are provided in the IB.

Fluarix is selected as an active control because it is licensed for the prevention of influenza disease in the adult population in the countries that will take part in this study. Enhanced quadrivalent influenza vaccines have not been considered for the ≥ 65 years old age group because they are not licensed or preferentially recommended in all participating countries.

Improved vaccine efficacy in adults ≥ 50 years old is needed given the increased morbidity and mortality in this population due to declining immunocompetence and increased burden of comorbid medical conditions.

4.4. End of Study Definition

A participant is considered to have completed the trial if they complete the final visit on Day 361 (Month 12) as shown in the SoE ([Table 1](#)).

The end of study is defined as completion of the last visit of the last participant in the trial or last scheduled procedure as shown in the SoE for the last participant in the trial globally.

5. STUDY POPULATION

Approximately 23,000 participants will be enrolled.

Prospective approval of protocol deviations to recruitment and enrollment criteria, also known as protocol waivers or exemptions, is not permitted.

5.1. Inclusion Criteria

Participants are eligible to be included in the study only if all the following criteria apply:

1. At least 50 years of age at the time of consent (Screening visit).
2. Investigator has assessed that the participant understands and is willing and physically able to comply with protocol-mandated follow-up, including all procedures.
3. Provide written informed consent for participation in this study, including all evaluations and procedures as specified by this protocol.
4. Females of nonchildbearing potential may be enrolled in the study. Nonchildbearing potential is defined as postmenopausal or permanently sterilized. Follicle-stimulating hormone may be measured at the discretion of the Investigator to confirm postmenopausal status (see additional information in [Section 11.2](#)).
5. Females of childbearing potential may be enrolled in the study if the participant fulfills all the following criteria:
 - Has a negative pregnancy test at the Screening visit and on the day of vaccination prior to study vaccine dose being administered on Day 1.
 - Has practiced adequate contraception or has abstained from all activities that could result in pregnancy for at least 28 days prior to the first dose (Day 1). Adequate female contraception is defined as consistent and correct use of a local health authority-approved contraceptive method in accordance with the product label.
 - Has agreed to continue adequate contraception through 90 days following study vaccine administration.

5.2. Exclusion Criteria

Participants are excluded from the study if any of the following criteria apply:

1. Close contact with someone with laboratory-confirmed influenza infection or with someone who has been treated with antiviral therapies for influenza (eg, Tamiflu®) within the past 5 days prior to the screening visit.
2. Close contact with someone with SARS-CoV-2 infection or COVID-19 as defined by the US CDC or has had a positive SARS-CoV-2 test in the past 10 days prior to the Screening visit.
3. Acutely ill or febrile (temperature $\geq 38.0^{\circ}\text{C}$ [100.4°F]) 72 hours prior to or at the Screening visit or Day 1. Participants meeting this criterion may be rescheduled within the 28-day screening window and will retain their initially assigned participant number.

4. History of a diagnosis or condition that, in the judgment of the Investigator, is clinically unstable or may affect participant safety, assessment of safety endpoints, assessment of immune response, or adherence to study procedures. Clinically unstable is defined as a diagnosis or condition requiring significant changes in management or medication within the 60 days prior to the Screening visit and includes ongoing workup of an undiagnosed illness that could lead to a new diagnosis or condition.
5. Reported history of congenital or acquired immunodeficiency, immunocompromising/ immunosuppressive condition, asplenia, or recurrent severe infections. The following conditions are permitted at the discretion of the Investigator:
 - Human immunodeficiency virus [HIV] positive participants on antiretroviral therapy with cluster of differentiation 4 count ≥ 350 cells/mm³ and HIV RNA ≤ 500 copies/mL within the past 12 months.
 - Immune-mediated diseases that are stable, for example, Hashimoto's thyroiditis and type 1 diabetes mellitus or conditions such as asthma, psoriasis, vitiligo, gout, alopecia areata, autoimmune ovarian failure that do not require systemic immunosuppressants per Exclusion Criterion 10.
6. Dermatologic conditions that could affect local solicited AR assessment of the injection site (eg, tattoos, vitiligo or psoriasis patches affecting skin over the deltoid area of the injection site).
7. Reported history of anaphylaxis or severe hypersensitivity reaction after receipt of any mRNA or influenza vaccines or any components of the mRNA or influenza vaccines, including egg protein.
8. Reported history of coagulopathy or bleeding disorder that is considered a contraindication to IM injection or phlebotomy.
9. Any medical, psychiatric, or occupational condition, including reported history of substance abuse, that, in the opinion of the Investigator, may pose additional risk due to participation in the study or that could interfere with the interpretation of study results.
10. Received systemic immunosuppressants for > 14 days in total within 180 days prior to the Screening visit (for glucocorticosteroids, ≥ 10 mg/day of prednisone or equivalent) or is anticipating the need for systemic immunosuppressive treatment at any time during participation in the study. Inhaled, nasal, intra-articular, and topical steroids are allowed.
11. Received any vaccine authorized or approved by local health agency ≤ 28 days prior to study intervention (Day 1) or plans to receive a vaccine authorized or approved by local health agency within 28 days before or after the study intervention.
12. Plans to receive a nonstudy influenza vaccine during the study from Day 1 to Day 181.
13. Is unaware whether they received an influenza vaccine in the previous influenza season.
14. Received a seasonal influenza vaccine or any other investigational influenza vaccine within 180 days prior to the Randomization Visit.
15. Tested positive for influenza by local health authority-approved testing methods within 180 days prior to the Randomization Visit.

16. Has been treated with antiviral therapies for influenza (eg, Tamiflu) within 180 days prior to the Randomization Visit.
17. History of myocarditis, pericarditis, or myopericarditis within 60 days prior to the Screening visit. Participants who have not returned to baseline after their convalescent period will also be excluded.
18. History of Guillain-Barre syndrome.
19. Received systemic immunoglobulins and long-acting biological therapies that affect immune responses (eg infliximab) or blood products within 90 days prior to the Screening visit or plans to receive them during the study.
20. Donated ≥ 450 mL of blood products within 28 days prior to the Screening visit or plans to donate blood products during the study.
21. Participated in an interventional clinical study within 28 days prior to the Screening visit based on the medical history interview or plans to do so while participating in this study.
Note: interventions such as counseling, biofeedback, and cognitive therapy are not exclusionary.
22. Participant is working or has worked as study personnel or is an immediate family member or household member of study personnel, study site staff, or Sponsor personnel.

5.3. Lifestyle Restrictions

Participants must not eat or drink anything hot or cold within 10 minutes before oral temperature is taken. Participants in the trial should defer vaccination with licensed seasonal influenza vaccine until after completion of the Day 181 visit, if seasonal influenza vaccine is available, and they have discussed with the Investigators and have chosen to receive it.

5.4. Screen Failures

Screen failures are defined as participants who consent to participate in the clinical trial but are not subsequently randomized. A minimal set of screen failure information is required to ensure transparent reporting of screen failure participants to meet the Consolidated Standards of Reporting Trials (CONSORT) publishing requirements and to respond to queries from regulatory authorities. Minimal information includes date of informed consent, demography, screen failure details, eligibility criteria, and information on any SAE, which may have occurred from the time informed consent was obtained to the time of withdrawal.

Individuals who do not meet the criteria for participation in this study (screen failures) may be rescreened 1 time if they will be eligible upon rescreening.

6. STUDY TREATMENT

Study interventions are all pre-specified, investigational and non-investigational medicinal products, medical devices and other interventions (eg, surgical and behavioral) intended to be administered to the study participants during the study conduct.

6.1. Study Intervention(s) Administered

All mRNAs are formulated in LNPs composed of 4 lipids (1 proprietary and 3 commercially available) and provided as a sterile liquid for injection, white-to-off-white dispersion in appearance, at a concentration of [REDACTED] mg/mL [REDACTED].

mRNA-1010 will be administered as a single IM injection dose at mRNA total dose level of [REDACTED] µg (see Table 4).

The active comparator administered in this study is a licensed quadrivalent inactivated seasonal influenza vaccine administered as a single IM injection (see Table 4).

Table 4: Study Interventions

Vaccination Group	Investigational Vaccine	Active Comparator
Intervention Name	mRNA-1010	Fluarix®/Influsplit®
Type	Vaccine	Vaccine
Unit Dose Strength	[REDACTED] µg (mRNA)	[REDACTED] µg (protein)
Dosage Level	Single dose of [REDACTED] mL	Single dose of [REDACTED] mL
Route of Administration	IM	IM
Physical Description	Sterile liquid for injection, white to off white dispersion	Sterile, colorless, and slightly opalescent suspension
Source	Provided centrally by the Sponsor	Hybrid – Potentially Centrally and Locally
Packaging and Labeling	mRNA-1010 will be provided in 2R glass vials. Each vial will be labeled as required per country requirement.	Active comparator will be provided in a prefilled syringe in a carton. Each carton will be labeled as required per country requirement.

Abbreviations: IM = intramuscular; mRNA = messenger ribonucleic acid.

6.2. Randomization and Blinding

Randomization will be performed using an Interactive Response Technology (IRT) system.

Approximately 23,000 participants will be randomized in a 1:1 ratio to receive a single dose of mRNA-1010 at [REDACTED] µg total mRNA or a single dose of the active comparator (Table 3).

Randomization will be stratified by age categories (≥ 50 to < 65 years or ≥ 65 years) and influenza vaccine status in the previous influenza season (received or not received) at the time of screening. At least 50% of enrollees will be ≥ 65 years old, including at least 10% who will be ≥ 75 years old.

As the appearance of the study interventions differ, enrollment will be observer blinded to the treatment assignment.

Dose preparation, administration, and accountability will be performed by designated unblinded site personnel who will not participate in any of the clinical study evaluations. The unblinded site personnel will prepare the dose out of view of the participant and the blinded site personnel.

The laboratory personnel in charge of immunogenicity testing will be blinded to the treatment assignment of the samples tested throughout the course of the study.

Except in the case of medical emergency, a participant's treatment should not be unblinded without the approval of the Sponsor. The treatment code should be broken only if the Investigator in charge of the participant feels that the case cannot be treated without knowing the identity of the study intervention. Instructions regarding emergency unblinding will be provided to the Investigator and are discussed in [Section 6.3.7](#).

The Investigator, clinic staff, study participants, site monitors, and Sponsor personnel (or its designees) will be blinded to the study intervention administered until the study database is locked and unblinded for the final analysis. At the interim analyses (see [Section 9.6.1](#)), pre-identified Sponsor team members and selected CRO team members will be unblinded to conduct the analyses. Study sites will remain blinded.

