9. STATISTICAL CONSIDERATIONS

9.1. Blinding and Responsibility for Analyses

This is an observer-blind study. The Investigator, clinic staff, study participants, site monitors, and Sponsor personnel (or its designees) will be blinded to the study intervention administered until the study database is locked and unblinded, with the following exceptions:

- Unblinded personnel (of limited number) will be assigned to vaccine accountability procedures and will prepare the study intervention for all participants. These personnel will have no study functions other than the study intervention management, documentation, accountability, preparation, and administration. They will not be involved in participant evaluations and will not reveal the identity of the study intervention to either the participant or the blinded clinic personnel involved in the conduct of the study unless this information is necessary in the case of an emergency.
- Unblinded clinic personnel will administer the study intervention. They will not be involved in assessments of any study endpoints.
- Unblinded site monitors, not involved in other aspects of monitoring, will be assigned as the study intervention accountability monitors. They will have responsibilities to ensure that sites are following all proper study intervention accountability, preparation, and administration procedures.
- An independent unblinded statistical and programming team will perform the preplanned interim analyses ([Section 9.5.4](#)). Sponsor team members will be pre-specified to be unblinded to the interim analyses results and will not communicate the results to the blinded Investigators, clinic staff, clinical monitors, or participants.
- The DSMB may review data, as appropriate, to safeguard the interests of clinical trial participants and to help ensure the integrity of the study.

The dosing assignment will be concealed by having the unblinded pharmacy personnel prepare the study intervention in a secure location that is not accessible or visible to other clinic staff. An opaque sleeve over the syringe used for injection will maintain the blind at the time of injection, as mRNA-1010 will look different from the active comparator. Only delegated unblinded clinic staff will conduct the injection procedure. Once the injection is completed, only the blinded clinic staff will perform further assessments and interact with the participants. Access to the randomization code will be strictly controlled at the pharmacy.

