9.6. Planned Analyses

9.6.1. Interim Analyses

There is one planned IA with data cut-off around the middle of February 2023 regardless of number of influenza cases accrued for the first null hypothesis to be tested to support the primary objective. The intent of the IA is for early detection of reliable evidence that rVE of mRNA-1010 is noninferior to the active comparator. The Lan-DeMets Pocock boundaries are used for calculating efficacy boundaries and to preserve the (1-sided) 2.5% Type I error rate over the IA and the final analysis (when the target number of cases have been observed), relative to the hypothesis:

$$H_0^1: HR \geq 1.1 \text{ (equivalently, rVE} \leq -10\%).$$

If NI is demonstrated at an IA, the subsequent final analysis will be considered supportive in nature for the NI claim. The DSMB will review the IA results and make recommendations to the Sponsor in terms of study results reporting and unblinding based on the boundaries of early efficacy as described in this section.

Table 8 summarizes the timing, number of cases, and decision guidance at each IA and final analysis.

Table 8: Interim Boundaries Using Lan-DeMets Pocock Spending Function, Calculation Based on the PP Set for the Endpoint Supporting the Primary Objective

Information Fraction (% of total #cases)	Number of Cases	Nominal Alpha (1-sided) ±	Efficacy Boundary Rejecting H_0 : rVE \leq -10%	Cumulative Probability (Crossing Efficacy Boundary if the True rVE = 25%)
IA (75% cases assumed)	274	2.07%	rVE \geq 14.0% (HR \leq 0.860)	87.1%
Final Analysis (100%)	365	1.2%	rVE \geq 13.2% (HR \leq 0.868)	93.7%

Abbreviations: HR = hazard ratio; IA: interim analysis; PP = per-protocol; rVE = relative vaccine efficacy.
 ±: actual nominal alpha may be adjusted based on the actual information fraction at individual IA(s).

The study will be considered positive (rVE has been demonstrate) if the *p-value* for rejecting HR \geq 1.1 is less than 2.07% based on the Lan-DeMets Pocock alpha spending function, provided that the IA is conducted exactly at 75% information fraction. The final analysis will be performed when approximately 365 cases have been observed in the PP Set. In the case that the early study success is not achieved, the study will be considered positive at the final analysis if the 1-sided *p-value* for rejecting HR \leq 1.1 is less than 1.2%.

[figure not shown]

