Except for the appropriately delegated unblinded pharmacists, vaccine administrators, clinical trial managers, and monitors, and selected Sponsor and CRO personnel to be unblinded per the study Data Blinding Plan (DBP), all other personnel involved in the conduct of the study will remain blinded until the study is completed at the end of the study, and after the database is cleaned and locked.

In addition to the routine study monitoring outlined in the protocol, an independent data and safety monitoring board (DSMB) will review the unblinded safety and efficacy data at IA, and the final analysis to safeguard the interests of clinical study participants and to enhance the integrity of the study. The DSMB will make recommendations to the Sponsor in terms of study results reporting and unblinding based on the efficacy success criteria as described in [Section 6.4](#) of this SAP.

More details of blinding and unblinding processes are specified in the study DBP.

5. Analysis Populations

Analysis populations for statistical analyses include the Randomization Set, Full Analysis Set (FAS), mITT Set, PP Set, Solicited Safety Set, and Safety Set.

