6.5. Planned Analyses

There is one planned IA with data cut-off around the middle of February 2023 regardless of number of influenza cases accrued for the primary NI hypothesis to be tested to support the primary objective. The intent of the IA is for early detection of reliable evidence that rVE of mRNA-1010 is noninferior to the active comparator. The Lan-DeMets Pocock boundaries are used for calculating efficacy boundaries and to preserve the (1-sided) 2.5% Type I error rate over the IA and the final analysis (when the target number of cases have been observed), relative to the hypothesis:

$$H_0^1: HR \geq 1.1 \text{ (equivalently, rVE} \leq -10\%).$$

If NI is demonstrated at an IA, the subsequent final analysis will be considered supportive in nature for the NI claim. The DSMB will review the IA results and make recommendations to the Sponsor in terms of study results reporting and unblinding based on the boundaries of early efficacy as described in this section.

In summary, one IA for the primary efficacy endpoints and a final efficacy analysis are planned in this study ([Table 4](#)). An EoS analysis may be performed in this study as described below.

- IA for the primary efficacy endpoint will be performed with data cut-off around the middle of February 2023 when it is projected that approximately 75% of the total cases (274 RT-PCR confirmed protocol-defined ILI cases across both treatment groups) would be observed in the PP Set. In the case that fewer cases are observed by middle of February, the IA will continue to be conducted during this timeframe due to seasonality considerations. The nominal alpha level to be spent at the IA and final analysis will be adjusted accordingly. The DSMB will review the unblinded IA results.
- The final efficacy analysis will be performed when approximately 365 cases across both treatment groups have been observed in the PP set.
- The EoS analysis may be performed when all study participants have completed the final visit on Day 361 (Month 12) or have withdrawn from the study. The study database will be cleaned and locked, and the study will be unblinded.

The RT-PCR confirmed ILI cases are counted when the first episode starts 14 days after the vaccination and up to Day 181/ Month 6 or at the end of the influenza season whichever ends later.

Table 4: Planned Analyses and Hypothesis Testing for the Primary Efficacy Endpoint

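### Protocol 6.2 ties the end of site and participant blinding to the case-driven final analysis, while Protocol 4.1 and the SAP carry it through study conduct; the passages must be reconciled

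*Protocol*

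**What the plan says.** Protocol 6.2 lists the investigator, clinic staff, participants, site monitors and Sponsor personnel, and says they "will be blinded to the study intervention administered until the study database is locked and unblinded for the final analysis". It then describes who is unblinded at the interim and adds "Study sites will remain blinded". No matching sentence covers the final analysis.

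Protocol 9.6.1 makes that analysis case-driven: "The final analysis will be performed when approximately 365 cases have been observed in the PP Set".

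Other parts of the protocol differ:

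- Section 4.1 says that the participant, the investigator and the clinical staff who do assessments "will not have access to the treatment assignment during the conduct of the study". The same paragraph refers to a planned study unblinding but does not date it.
- Section 4.2 allows a limited number of Sponsor or CRO staff to be unblinded for DSMB safety analyses and for a primary analysis, a term that 9.6 does not define.
- Section 9.1 keeps the blind "until the study database is locked and unblinded, with the following exceptions", without naming an analysis. Its bullet on the independent unblinded statistical team covers the interim analyses only.

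The SAP is clearer. Section 4.5 gives both the interim and the final analysis to an independent unblinded CRO team, and allows a separate unblinded Sponsor team for regulatory submissions. Apart from the named unblinded roles, "all other personnel involved in the conduct of the study will remain blinded until the study is completed at the end of the study". Section 6.5 separates the 365-case final analysis from an optional end-of-study (EoS) analysis, held once everyone has either reached Day 361 or left. It attaches the lock to the latter: "The study database will be cleaned and locked, and the study will be unblinded".

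**The concern.** Protocol 6.2 is the section devoted to blinding, and it sets a release point that can fall months before a participant's last visit. The SAP sets a later one.

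SAEs, MAAEs, AESIs and AEs leading to discontinuation are primary safety endpoints through Day 361 (Protocol Table 2). An MAAE exists only if the participant seeks care (Protocol 8.10.4), and causality is the investigator's judgment (8.10.8). Protocol 5.3 also contemplates licensed influenza vaccination after the Day 181 visit. Knowledge of the arm could therefore affect reporting, attribution, later vaccination and retention differently in the two groups. The documents give no figure for how large such a difference would be. The exploratory outcomes that run to Day 361, such as all-cause hospitalization, would be exposed in the same way.

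The formal efficacy test would not be affected, because its data are cut before the unblinding in question. An unblinding that has happened cannot be undone, so the wording should be settled beforehand.

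**Working it through.** 1. **Can the passages be reconciled as written?** Protocol 6.2 ends the blind at the lock for the final analysis. SAP 4.5 ends it at completion of the study. Both can hold only if the two analyses share one lock. SAP 6.5.3 says they may be combined if timing allows, so a shared lock is possible but not assured. The SAP's precedence clause (Section 1) refers to methods and does not clearly reach site blinding. SAP Section 7 records no change from the protocol's planned analyses.

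2. **Is the final analysis tied to Day 361?** The inputs, from Protocol 9.3, are 23,000 participants randomized 1:1 (11,500 per arm), a 2% comparator attack rate, 25% rVE (so 2% × 0.75 = 1.5% on mRNA-1010), and 10% not evaluable for the PP Set.
   - Expected PP cases = 11,500 × 0.90 × (0.020 + 0.015) = 362, against 365 stated.
   - Expected mITT cases, with 4% not evaluable = 11,500 × 0.96 × 0.035 = 386, as stated.
   - The interim is projected for mid-February 2023 at 274 cases, and 274/365 = 75%. That leaves 365 − 274 = 91 cases to accrue.

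   The trigger reproduces as a case count. Nothing in it refers to Day 361, and no calendar date is given for the final analysis.

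3. **Share of follow-up exposed under 6.2 read literally.** For unblinding on study day d, the open-label share of Day 1–361 follow-up time is (361 − d)/361.
   - d = 120: 241/361 = 67%
   - d = 181: 180/361 = 50%
   - d = 241: 120/361 = 33%
   - d = 271: 90/361 = 25%
   - d = 361 or later: 0%

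4. **Calendar range.** Both dates here are assumptions: vaccination between 15 September and 15 December 2022, and the unblinding date shown. Study day is the date minus the vaccination date plus 1 (SAP 6.1.4).

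| Unblinding (assumed) | Study day, earliest to latest vaccinated | Open-label share |
|---|---|---|
| 15 March 2023 | 182 to 91 | 50% to 75% |
| 30 April 2023 | 228 to 137 | 37% to 62% |
| 30 June 2023 | 289 to 198 | 20% to 45% |
| 31 July 2023 | 320 to 229 | 11% to 37% |
| 31 March 2024 | past 361 | 0% |

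   The last row is the case in which accrual runs into a second season, which Protocol 4.1 allows. The 0% applies to first-season participants; for anyone enrolled later, the formula in step 3 applies from their own Day 1.

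5. **Which endpoints are exposed.** In every dated row the unblinding falls on Day 91 or later. Solicited ARs (7 days) and unsolicited AEs (28 days) are complete by then. Only the four endpoints collected through Day 361 are exposed.

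**The case against.** The strongest defense is that the intended design is plain and that 6.2 is one loose phrase. Protocol 4.1 tells sites directly that they have no access to assignments during conduct. Section 4.2 limits who is unblinded for the primary analysis. Section 6.2 sets a minimum blinding period and does not tell anyone to release codes. Sections 6.2 and 6.3.7 require Sponsor approval for unblinding outside an emergency, and the Schedule of Events contains no unblinding contact. The SAP runs the final analysis behind a firewall, and operational detail sits in a Data Blinding Plan that is not among these documents. SAP 6.1.7 also makes the 28-day window the primary analysis period for safety other than solicited ARs. Both arms receive an active vaccine, and no study product is offered afterwards.

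Most of this stands, and it limits the claim. A reader might infer that the protocol as a whole ends blinding at the final analysis; Section 4.1 contradicts that. A reader might infer that sites will be open-label; the documents show only that 6.2 would permit it. A reader might also infer that a third to a half of the safety endpoints would be unblinded. That range is a share of follow-up time, it requires unblinding between about Day 181 and Day 241, and the short-term endpoints lie outside it.

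The defense does not remove the conflict. Section 4.1 pointing the other way makes the protocol inconsistent with itself. Section 9.1 does not settle which lock is meant, and its independent unblinded team is not assigned to the final analysis. Combining the final and EoS analyses is optional.

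**Conclusion.** The inconsistency is real and follows from the text without any assumption: Protocol 6.2 names an earlier end of blinding than Protocol 4.1 and SAP 4.5 and 6.5 do. Taken literally, it would allow sites and participants to learn their arm before Day 361 whenever the final analysis precedes the EoS analysis.

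The size cannot be fixed from the documents. Across the assumed dates it runs from 0% to about 75% of follow-up time, and it is 0% if the two analyses share a lock. It concerns SAEs, MAAEs, AESIs and AEs leading to discontinuation. This should be corrected, but it is a wording conflict in a design whose intent appears to be blinding to the end, and it does not show that the blind will be broken.

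**What to change.** In Protocol 6.2, replace the reference to the final analysis with end of study: every participant has completed Day 361 or withdrawn, and the database is locked. State that sites and participants stay blinded at both the interim and the final efficacy analysis.

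Align the related text:

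- 4.1: define the planned study unblinding as that same point.
- 4.2: say which analysis its primary analysis is.
- 9.1: name the lock that is meant, and extend the independent unblinded team to the final analysis. The cross-reference in that bullet leads to exploratory analyses (9.5.4) and should lead to 9.6.1.
- Carry over the SAP 4.5 arrangement of an independent unblinded CRO team and a Sponsor submission team kept apart from study conduct.

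Tie the end of blinding to end of study and not to the EoS analysis, which the SAP says only may be performed.

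The cost is a few sentences in the next amendment. SAP 4.5 already provides the separate teams, so no further staff are needed. The downside is that participants learn their arm some months later.
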